6.2. Statistical Tests

All formal statistical tests of treatment effects will not be done. Point estimates will be accompanied with two-sided 95% CIs where applicable.

7. DATA CONVENTIONS

7.1. Analysis Variable Definitions

7.1.1. Study Subjects

7.1.1.1. Demographic and Other Baseline Characteristics

(1) BMI

BMI will be recalculated using the formula below and reported to 1dp.

$$\text{BMI (kg/m}^2\text{)} = \text{weight at screening (kg)} / \{\text{height at screening (m)}\}^2$$

(2) Age(years)

If (month of date of consent > month of date of birth) or (month of date of consent = month of date of birth and day of date of consent >= day of date of birth), then Age (years) = year of date of consent - year of date of birth

if else case, then Age (years) = year of date of consent - year of date of birth -1.

(3) Time since osteoarthritis diagnosis (years)

Time since osteoarthritis diagnosis will be calculated using the formula below and reported to 1dp.

If (month of date of consent > month of osteoarthritis diagnosis) or (month of date of consent = month of date osteoarthritis diagnosis, and day of date of consent >= day of date of osteoarthritis diagnosis), then Time since osteoarthritis diagnosis (years) = (date of consent - date of osteoarthritis diagnosis) / 365.25*

if else case, then Time since osteoarthritis diagnosis (years) = (date of consent - date osteoarthritis diagnosis - 1) / 365.25*.

* 1 year = 365.25 days

Impute date of osteoarthritis diagnosis as the earliest possible date (i.e. first day of month if day is unknown or 1st January if day and month are unknown).

(4) Renal function (stage 1, stage 2, stage 3, stage 4, stage 5)

The stages of renal function are defined by the FDA guidance as follows^[1] :

Stage	Description ^b	eGFR ^c (mL/min/1.73m ²)
1	Control (normal) GFR	≥ 90
2	Mild decrease in GFR	60-89
3	Moderate decrease in GFR	30-59
4	Severe decrease in GFR	15-29
5	End Stage Renal Disease (ESRD)	<15 not on dialysis Requiring dialysis

7.1.1.2. Medical History

Medical history will be coded according to the MedDRA version 20.1.

7.1.1.3. Prior or Concomitant Medication

Medications will be coded according to the WHO Drug Dictionary (WHO-DD) Sep 2017 B3 version.

(1) Prior Medication

Prior medications are defined as medications starting prior to the first dose of study drug.

(2) Concomitant Medication

Medications that are on-going or start after the first intake of study drug are classified as "Concomitant".

Assesment period is defined as the time from first dose of investigational product up to 28 days after the last dose of investigational product.

(3) Post-treatment Medication

Medications that are start after on-treatment period are classified as "Post-treatment Medication".

7.1.1.4. Treatment Duration, Treatment and Post-Treatment Observation Duration and Compliance

(1) Treatment Duration

1) Treatment duration (days) = The date of last study drug injection - the date of the first study drug injection + 28.

2) Criteria for pre-defined limit

Treatment duration period ≥ 1 day, ≥ 29 days, ≥ 57 days, ≥ 85 days, ≥ 113 days, ≥ 141 days, ≥ 169 days, ≥ 197 days, ≥ 225 days, ≥ 253 days, ≥ 281 days and ≥ 309 days

(2) Treatment and Post-Treatment Observation Duration

1) Treatment and Post-Treatment Observation duration (days) = Date of last study visit [up to end of the post treatment observation period] – date of first study drug dose).

2) Criteria for pre-defined limit

Treatment and Post-Treatment Observation duration period ≥ 1 day, ≥ 29 days, ≥ 57 days, ≥ 85 days, ≥ 113 days, ≥ 141 days and ≥ 169 days, ≥ 197 days, ≥ 225 days, ≥ 253 days, ≥ 281 days, ≥ 309 days, ≥ 337 days, ≥ 365 days, ≥ 393 days, ≥ 421 days and ≥ 449 days

(3) Treatment Compliance

1) Treatment compliance will be calculated using the formula below and reported to 1dp.

MT-5547

Treatment compliance(%) = (Number of injections of study drug during exposure period) / (Number of planned injections of study drug during exposure period on or before the time that the subject discontinues from the study) x 100%

Naproxen

Treatment compliance(%) = (Number of adherence of naproxen during exposure period) /

(Number of planned adherence of naproxen during exposure period on or before the time that the subject discontinues from the study) x 100%

2) Criteria for pre-defined limit

MT-5547

the number of injections of study drug: 1, 2, 3, 4, 5, 6, 7, 8, 9, 10, 11 and 12

the number of self-injection of study drug: 1, 2, 3, 4, 5 and 6

7.1.2. Efficacy assessments

7.1.2.1. WOMAC pain subscale score

WOMAC pain subscale score

$$= \frac{\text{sum of items from Section A 1 to Section A5 in questionnaire}}{5}$$

7.1.2.2. WOMAC physical function subscale score

WOMAC physical function subscale score

$$= \frac{\text{sum of items from Section C 8 to Section C24 in questionnaire}}{17}$$

7.1.2.3. WOMAC stiffness subscale score

$$\text{WOMAC stiffness subscale score} = \frac{\text{Section B 6 + Section B7 in questionnaire}}{2}$$

7.1.2.4. WOMAC total score

$$\text{WOMAC total score} = \frac{\text{sum of items from Section A1 to Section C24 in questionnaire}}{24}$$

7.1.2.5. SF-36 / EQ-5D-5L

- SF-36

Physical, Mental and Role social component summary will be calculated considering factor coefficients based on the 1995 Japan National Survey. The derivation of 8 subscales and three component is detailed in appendix 1.

- EQ-5D-5L

Utility Index Score will be calculated using the formula and Table below.^[1]

Utility Index Score

= 1 + [Estimation of the constant term(if all answer is not 1)]

+ [Sum of "estimation of coefficients corresponding to answer other than 1"]

[figure not shown]
Item	Level	Estimation	Standard Error	P-value
Mo	Intercept	-0.060924	0.013625	<0.0001
	2	-0.063865	0.008996	<0.0001
	3	-0.112618	0.009287	<0.0001
	4	-0.179043	0.010231	<0.0001
	5	-0.242916	0.009425	<0.0001
Sc	2	-0.043632	0.008931	<0.0001
	3	-0.076660	0.009972	<0.0001
	4	-0.124265	0.010129	<0.0001
	5	-0.159659	0.008924	<0.0001
	2	-0.050407	0.009205	<0.0001
Ua	3	-0.091131	0.010005	<0.0001
	4	-0.147929	0.009744	<0.0001
	5	-0.174786	0.009115	<0.0001
	2	-0.044545	0.008354	<0.0001
	3	-0.068178	0.010052	<0.0001
Pd	4	-0.131436	0.008985	<0.0001
	5	-0.191203	0.009604	<0.0001
	2	-0.071779	0.009701	<0.0001
	3	-0.110496	0.010863	<0.0001
	4	-0.168171	0.009850	<0.0001
Ad	5	-0.195961	0.009164	<0.0001

Mo: mobility, Sc: self-care, Ua: usual activities,

Pd: pain/discomfort, Ad: anxiety/depression

e.g) If answer is [1 1 1 1 1], Utility Index Score is = $1 + 0 + 0 = 1$. If answer is [1 1 3 2 1], Utility Index Score is = $1 + (-0.060924) + (-0.091131 - 0.044545) = 0.8034$.

7.1.2.6. Response rate based on the OMERACT-OARSI criteria

Note that the criteria in the diagram above are based on standardized score between 0 and 100. For this study, WOMAC pain and physical function subscale score are between 0 and 10, so the absolute change required for response is the required change in the diagram above divided by 10; PGA is 1, 2, 3, 4 or 5, so the absolute change required for response is at least 1 point.

7.1.2.7. Rescue Medication

Baseline amount of rescue medication is defined as the average of the non-missing values during 7 days prior to taking study drug. For each week, the average of the non-missing values between date collected WOMAC and next date collected WOMAC will be used.

7.1.3. Safety Assessments

The on-treatment period is defined as the time from first dose of investigational product up to 28 days after the last dose of investigational product.

The post-treatment period is defined as the time after the on-treatment period to the end of the post treatment observation period or early termination date.

7.1.3.1. Adverse Events

Adverse events will be coded according to the MedDRA version 20.1

(1) Treatment Emergent Adverse Events/ Treatment Emergent Serious Adverse Events (TEAEs/TESAEs)

An AE/SAE is classified as treatment emergent if it newly occurred after the first dose of study drug or if a pre-dose event increases in severity following the first dose of study drug during on-treatment period.

(2) Post-Treatment Adverse Events/ Treatment Serious Adverse Events

An AE/SAE is classified as post-treatment if it newly occurred after the on-treatment period or if the event after the on-treatment period increases in severity.

(3) Adverse Drug Reaction

A TEAE is considered “adverse drug reaction” if it has been assessed as having a “reasonable possibility” in relationship to the study drug.

(4) Adverse Event of Special Interest(AESI)

Adjudicated arthropathy(AA), sympathetic nervous system dysfunction, altered peripheral sensation, destructive arthropathy(DA) are defined as adverse events of special interest (AESI) for the sake of investigating the safety profile of MT-5547.

(5) Identified and Potential Adverse Events

Following are defined as identified and potential adverse event for the sake of investigating the safety profile of MT-5547.

- Arthralgia related event
 - (PT) Arthralgia
 - (PT) Osteoarthritis
 - (PT) Arthritis
 - (PT) Joint stiffness
 - (PT) Joint swelling
 - (PT) Joint effusion
 - (PT) Synovitis
- Bone fractures related event
 - Any PT containing “fracture” but excluding Tooth Fracture and Subchondral Insufficiency fracture (that have been identified to be AAs)
- Joint swelling related event
 - (PT) Joint Swelling
 - (PT) Joint Effusion
- Altered peripheral sensation related event
 - (HLGT) Peripheral Neuropathies
 - (HLT) Paraesthesia and dysaesthesia
 - (HLT) Sensory abnormalities NEC
 - (PT) Myalgia
 - (PT) Hyperreflexia
 - (PT) Hyporeflexia
 - (PT) Areflexia

- Sympathetic nervous system dysfunction related event
 - (HLT) Autonomic nervous system disorders
 - (HLT) Cardiac conduction disorders
 - (PT) Syncope
- Hypersensitivity / anaphylaxis related event
 - (SMQ) Angioedema
 - (SMQ) Anaphylactic reaction
 - (SMQ) Hypersensitivity
 - (PT) Erythema
 - (PT) Prurigo
 - (PT) Pruritus
 - (PT) Pruritus Generalised
 - (PT) Rash Papular

(6) Duration of Adverse Events

Duration of Adverse Events (days) = AE stop date – AE start date + 1

(7) Incidence Rate (per 100 patient-years)

For patients with events, number of patient years is calculated up to the date of the first event and for patients without event, it corresponds to the length of the study observation period.

Incidence Rate will be calculated using the formula.

Incidence Rate = the number of patients with event × 100 / sum of observation periods for all patients (days) × 365.25*

* 1 year = 365.25 days

7.1.3.2. Laboratory Tests

Listing of reference value in each laboratory parameters is detailed in appendix 3

(1) The Estimated Glomerular Filtration Rate (eGFR)

eGFR will be calculated as follows and reported to 1 dp.

$$\text{eGFR} = 141 \times \min(S_{\text{Cr}}/\kappa, 1)^\alpha \times \max(S_{\text{Cr}}/\kappa, 1)^{-1.209} \times 0.993^{\text{Age}} \times 1.018 \text{ [if female]} \times 1.159 \text{ [if Black]}$$

S_{Cr} (standardized serum creatinine) = mg/dL

κ = 0.7 (females) or 0.9 (males)

α = -0.329 (females) or -0.411 (males)

\min = indicates the minimum of S_{Cr}/κ or 1

max = indicates the maximum of S_{Cr}/κ or 1

Age = years

(2) Laboratory values below the limit of quantification

1/2 LLOQ (lower limit of quantification) will be used for BLQ (below the limit of quantification) data in summary statistics. ULOQ (upper limit of quantification) will be used for over the limit of quantification data in summary statistics.

(3) Criteria for pre-defined

Potentially clinically significant values (PCSV) ranges will be applied to the laboratory test values as applicable (see Appendix 2 for PCSV definitions).

7.1.3.3. Vital Signs

(1) Criteria for pre-defined

Potentially clinically significant values (PCSV) ranges will be applied to the vital sign parameter values as applicable (see Appendix 2 for PCSV definitions).

7.1.3.4. ECG

(1) Criteria for pre-defined

Potentially clinically significant values (PCSV) ranges will be applied to the ECG parameter values as applicable (see Appendix 2 for PCSV definitions).

(2) QTcF

QTcF will be calculated as follows and reported to 1 dp.

QTcF (msec) = $QT/RR^{1/3}$

RR = 60/HR

7.1.4. Pharmacokinetics Evaluation

7.1.4.1. MT-5547 Concentrations in Serum

For the calculation of the summary statistics, concentration values reported as below the limit of quantification (BLQ) will be set to 0. In the log-scaled figures, concentrations below the LLOQ imputed as LLOQ/2. The lower limit of quantification (LLOQ) is 7.8 ng/mL in neat human serum.

7.1.4.2. Anti-Drug Antibodies in Serum

Anti-drug antibody variables will include ADA status (positive or negative) and titer as follows:

- Total subjects negative in the ADA assay analyzed at all time points
- Pre-existing immunoreactivity - a positive ADA response at baseline with all post-dose

ADA results negative, or a positive ADA response at baseline with all post-dose ADA responses less than 9-fold over baseline titer levels.

- Treatment emergent - defined as any post-dose positive ADA response when baseline results are negative
 - Persistent - A positive result in the ADA assay detected in 2 consecutive post baseline samples, separated by at least 16-week period [based on nominal sampling time], with no ADA-negative results in-between, regardless of any missing samples
 - Indeterminate - A positive result in the ADA assay at the last collection time point analyzed only, regardless of any missing samples
 - Transient - Not persistent or indeterminate regardless of any missing samples
- Treatment boosted - defined as any post-dose positive ADA response that is at least 9-fold over the baseline level when baseline is positive in the ADA assay
- Titer Values
 - Titer category: low (titer <1,000); moderate (1,000≤ titer ≤10,000); high (titer >10,000)
- Neutralizing ADA activity for samples positive in the ADA assay

7.3. Data Handling Convention for Missing Data

(1) Non-PK related

Efficacy:

WOMAC

WOMAC scores will be computed when one pain, one stiffness, or 1-3 physical function items are missing. The missing items will be imputed by the mean of available items within the same subscale. The scores will be set to missing if more items are missing.

SF-36 / EQ-5D-5L

- SF-36 subscale scores will be computed if at least 50% of items are available. The missing items will be imputed by the mean of available items.
- EQ-5D-5L index will be set to missing if any of the 5 dimensions is missing.

Rescue Medication

If there is no date collected WOMAC, nominal date will be used.

Safety:

Adverse events

If severity or relationship is found to be missing the most severe occurrence will be imputed for the summary of interest.

For AE start missing or partial dates, the AE will be treated as TEAE if it cannot be determined to be a non-TEAE.

Laboratory test

Regarding hyaline casts and epithelial cells, set "Null" for blanks(= not detected) with date data.

Orthostatic Blood Pressure

If a retest is performed, the initial value should be compared with the retest value, and the value with the worst value should be used.

Other safety:

For safety summaries, only observed data will be used. If a value is indeterminate or a reference

value because of a problem with a test sample, then this value will be handled as a missing value.

(2) PK related

For PK summaries, only observed data will be used. Missing PK data will not be imputed. The PK data handling will be confirmed during blinded data review (BDR). PK data that are considered "invalid" will be flagged in the listing. Due to the nature of PK data, some issues may only be discovered after PK data are unblinded. Should new issues identified post unblinding, and new data handling rules would have to be applied, a separate PK data handling document will be produced to provide detailed rationale and decision making. If there is clear evidence that PK sample handling errors or other factors identified after data unblinding and these errors have led to unexpected erroneous data, then these erroneous data will be regarded as "invalid", full explanations will be given in the PK data handling document.

8. STATISTICAL METHODOLOGY

8.1. Study Subjects

8.1.1. Subject Disposition

Screened subject disposition will be summarized on the all subjects. Randomized subject disposition will be summarized by treatment group, combined MT-5547 and overall on the randomized population. Randomization details will be listed on the randomized population. Subject disposition will be listed on the randomized population.

8.1.2. Analysis Populations

Analysis populations will be summarized by treatment group, combined MT-5547 and overall on the randomized population. Analysis populations will be listed on the randomized population.

8.1.3. Site Enrollment

Investigator enrollment will be summarized by treatment group and overall on the randomized population.

8.1.4. Demographic and Other Baseline Characteristics

The following demographic and other baseline characteristics will be used.

	category	Descriptive
Sex	Male, Female	
Age(years)	<65, >=65	Yes
Height(cm)		Yes

Weight(kg)		Yes
BMI(kg/m2)	<25, >=25 and <30, >=30	Yes
Race	Japanese, other	
Time since OA diagnosis (years)	<1, >=1 and <5, >=5 and <10, >=10	Yes
Complication	Yes, No	
Index Joint	Knee, Hip	
K-L score	1, 2, 3, 4	
Renal function	stage 1, stage 2, stage 3, stage 4, stage 5	
WOMAC pain subscale score	<6 ≥6	Yes
WOMAC Physical function subscale score	<6 ≥6	Yes
PGA	1, 2, 3, 4, 5	Yes
Pain site	Right Knee, Left Knee, Right Hip, Left Hip, Right Shoulder, Left Shoulder	
Pretreatment drug	NSAIDs(Systemic use), NSAIDs(Topical use), Acetaminophen, Opioid, Monoamine reuptake inhibitor, Hyaluronic acid, Pregabalin, Herbal medicine, Other	
NSAIDs Inadequate Pain Relief	Yes, No	
NSAIDs Intolerance	Yes, No	
Ever taken Opioid for Pain due to OA	Yes, No	
Opioid Inadequate Pain Relief	Yes, No	
Opioid Intolerance	Yes, No	
Ever taken Acetaminophen for Pain due to OA	Yes, No	
Acetaminophen Inadequate Pain Relief	Yes, No	
Acetaminophen Intolerance	Yes, No	

NSAID + Opioid + Acetaminophen Inadequate Pain Relief	Yes, No	
---	---------	--

Demographic and other baseline characteristics will be summarized by treatment group, and before the protocol amendment and after the protocol amendment on the mFAS population. Demographic and other baseline characteristics will be summarized by treatment group, combined MT-5547 and overall on the FAS population. Demographic and other baseline characteristics will be listed on the randomized population.

8.1.5. Medical History

Medical history will be summarized by treatment group, combined MT-5547 and overall on the FAS population. Medical history will be listed on the randomized population.

8.1.6. Radiograph eligibility data

Radiograph eligibility data at pre-treatment will be summarized by treatment group, combined MT-5547 and overall on the FAS population. Radiograph data will be listed on the randomized population.

8.1.7. Prior or Concomitant Medications

Prior medication used for OA and concomitant medication and post-treatment medication will be summarized separately by treatment group and combined MT-5547 on the FAS population. All prior and concomitant medication and concomitant therapy and post-treatment therapy will be listed on the randomized population.

8.1.8. Treatment Duration, Treatment and Post-Treatment Observation Duration and Compliance

Treatment duration and treatment and post-treatment observation duration will be summarized by treatment group and combined MT-5547 on the SAF population. Treatment compliance of MT-5547 and naproxen will be summarized by treatment group and combined MT-5547 on the FAS population. The number of MT-5547 self-injection will be summarized by the principal investigator or sub-investigator and the self-injections and by MT-5547 treatment group on the mFAS population. Treatment duration, treatment and post-treatment observation duration and compliance will be listed on the randomized population. Study drug interruptions will be listed on the randomized population.

8.2. Efficacy Assessments

Efficacy assessment will be summarized by treatment group on the mFAS population.

[figure not shown]
8.2.1. Other Efficacy Endpoints

WOMAC pain subscale score, WOMAC physical function subscale score, WOMAC

stiffness subscale score, WOMAC total score , WOMAC individual score and PGA

For the changes from baseline at each assessment time point in the WOMAC pain subscale score, the WOMAC physical function subscale score, the WOMAC stiffness subscale score, the WOMAC total score, WOMAC individual score and PGA, the analysis will be tested using the estimator of mixed effect model for repeated measurement (MMRM) approach. The model will include the treatment group, measurement time point, treatment group and measurement time point interaction, stratification factor K-L grade (2-3 or 4), and stratification factor evaluated joint (knee or hip) as factors, and the corresponding baseline and baseline and measurement time point interaction as covariates. The within-subject correlation structure will be unstructured, and the denominator degrees of freedom for the test statistics of estimated parameters will be approximated using the Kenward-Roger method. In case the model will not converge with the unstructured covariance structure, Heterogeneous Autoregressive (1) (ARH[1]), Heterogeneous Compound Symmetry (CSH), Autoregressive (1) (AR[1]) or Compound Symmetry(CS) covariance structure will be used instead in this order. MMRM that assumes that the missing mechanism is missing at random (MAR) is an analysis method in which missing values are not replaced. This model will be used to estimate the treatment effect in the mFAS when subjects continue receiving treatment through Week 68.

The sample SAS code planned for the analysis is outlined below.

WOMAC score and PGA will be listed. In addition, change from baseline to week 68 in WOMAC pain subscale score, WOMAC physical function subscale score and PGA will be graphed by visit.

SF-36 / EQ-5D-5L

For the changes from baseline at each assessment time point in SF-36 eight subscale summary scores and three component summary scores / EQ-5D-5L visual analogue scale(VAS) and utility index scores, the same analysis method (MMRM) as above will be analyzed. SF-36 / EQ-5D-5L will be listed.

Proportions of subjects with improvement of 30%, 50%, 70% and 90% at each assessment time point compared to baseline in WOMAC pain subscale score, WOMAC physical function subscale score and improvement of 30%, 50% and 70% at each assessment time point compared to baseline in PGA

A generalized linear mixed-effects model (GLMM) by logit type for response variable will be used to evaluate these binary response variables. The denominator degrees of freedom for the test statistics of estimated parameters will be approximated using the Kenward-Roger method. The estimated response rate for each treatment group and placebo group and 95% confidence interval of the odds ratio of each of the MT-5547 1 mg q4w and MT-5547 1 mg q8w groups compared to the placebo group in each binary response variables will be calculated using this GLMM approach.

- The covariates: baseline and the interaction of baseline and measurement time point.
- The fixed factors: Treatment group, measurement time point, the interaction of treatment group and measurement time point, K-L grade (2-3 or 4), and evaluated joint location (knee or hip)
- Random factors: Measurement time point for subject specific with covariance structure of unstructured

The sample SAS code planned for the analysis is outlined below.

[REDACTED]

Response rate based on the OMERACT-OARSI criteria at each assessment time point compared to baseline

Responder analyses for OMERACT-OARSI will be summarized at each assessment time point using the same GLMM approach in previous model.

Proportion subjects who used rescue medication

The proportion of subjects taking rescue medication in baseline and up to week 48 will be summarized by treatment group. The proportion of days on rescue medication use during treatment period will be summarized at each week by treatment group. Number of average usage of rescue medication will be summarized at each week by treatment group.

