8.2.1. Primary Efficacy Endpoint

The change in the WOMAC pain subscale score from baseline to Week 16 will be summarized and plotted by treatment group.

Primary analysis method

The primary analysis will be tested using the estimator of mixed effect model for repeated measurement (MMRM) approach. The model will include the treatment group, measurement time point, treatment group and measurement time point interaction, stratification factor K-L grade (2-3 or 4), and stratification factor evaluated joint (knee or hip) as factors, and the baseline and baseline and measurement time point interaction as covariates. The within-subject correlation structure will be unstructured, and the denominator degrees of freedom for the test statistics of estimated parameters will be approximated using the Kenward-Roger method. In case the model will not converge with the unstructured covariance structure, Heterogeneous Autoregressive (1) (ARH[1]), Heterogeneous Compound Symmetry (CSH), Autoregressive (1) (AR[1]) or Compound Symmetry(CS) covariance structure will be used instead in this order.

- Evaluation on 1 mg q4w group

[figure not shown]
With pooling the data on 1 mg q4w and placebo obtained before and after the protocol amendment (Ver. 04.00.00000), the least square mean, standard error, P value, and 95% confidence interval of the difference between each of the MT-5547 1 mg q4w and the placebo group in the change in the WOMAC pain subscale score from baseline to Week 16 will be calculated using the MMRM approach.

- Evaluation on 1 mg q8w group

Using only the data obtained after the protocol amendment (Ver. 04.00.00000), the least square mean, standard error, P value, and 95% confidence interval of the difference between each of the MT-5547 1 mg q4w, MT-5547 1 mg q8w and the placebo groups in the change in the WOMAC pain subscale score from baseline to Week 16 will be calculated using the MMRM approach.

MMRM that assumes that the missing mechanism is missing at random (MAR) is an analysis method in which missing values are not replaced. This model will be used to estimate the treatment effect in the mFAS when subjects continue receiving treatment through Week 16.

The SAS code planned for the analysis is outlined below.

Sensitivity analyses

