3.3. Sample Size and Power Considerations

The original target sample size is 568 treated subjects (142 subjects per group)
(MT-5547 1 mg q4w group: 142 subjects; MT-5547 3 mg q4w group: 142 subjects; MT-5547 6 mg q8w group: 142 subjects; placebo group: 142 subjects)

After initiation of this study, based on the recommendations from the IDMC, the 3 mg q4w and 6 mg q8w groups were removed and 1 mg q8w group was newly added to the treatment groups.

The amended target sample size is 506 treated subjects, including the subjects who were randomized to 1 mg q4w/placebo groups before the amendment (approximately 40 subjects per group) and the subjects who are randomized to 1 mg q4w/1 mg q8w/placebo groups with the ratio of 1:1:1 after the amendment (142 subjects per group).

(MT-5547 1 mg q4w group: 182 subjects; MT-5547 1 mg q8w group: 142 subjects; placebo group: 182 subjects)

In addition, 57 patients each were enrolled in the MT-5547 3 mg q4w and 6 mg q8w groups prior to the protocol amendment (Ver. 04.00.00000) and were discontinued from study drug based on the recommendations from the IDMC. Thus, enrollment of 563 subjects is planned for this study in total.

The original rationale at the initiation of the study

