the change from baseline in the physical function subscale score at Week 16 with an associated standard deviation of 2.5 based on the original rationale at the initiation of the study, the number of patients per group after the protocol amendment (Ver. 04.00.00000) is planned to 142 subjects per group. The structure of statistical hypotheses have been changed due to the removal of 3 mg q4w / 6 mg q8w groups and the addition of 1 mg q8w. It is noted that approximately 40 subjects per group were randomized to 1 mg q4w / placebo groups before the amendment. For evaluation on 1 mg q4w, since subjects are randomized to 1 mg q4w / placebo at the same time with the same ratio of 1:1 regardless of pre- or post- amendment, analyses will be performed with pooled comparable data including pre- and post- amendment data on 1 mg q4w / placebo (1 mg q4w group: 182 subjects; placebo group: 182 subjects). For evaluation on 1 mg q8w, analyses will be performed with only the post-amendment data (1 mg q4w group: 142 subjects; 1 mg q8w group: 142 subjects; placebo group: 142 subjects). For four null hypotheses, based on multiplicity adjustment based on a gate keeping method using a graphical approach (Figure 8.2.1-1 in section 8.2.1 of SAP for database at week 16), the power for MT-5547 1 mg SC q4w and 1 mg SC q8w will be 97% and 92% for the primary endpoint, 94% and 87% for the key secondary endpoint, respectively.

Table 3.1-1 Change From Baseline at Week 16 in the WOMAC Pain and Physical Function Subscale Scores

	REGN Study R475-PN-1227					REGN Study R475-PN-0901			
	Placebo (N=83)	MT-5547 1 mg (N=85)	MT-5547 3 mg (N=84)	MT-5547 6mg (N=85)	MT-5547 9 mg (N=84)	Placebo (N=55)	MT-5547 0.03 mg/kg (N=53)	MT-5547 0.1 mg/kg (N=53)	MT-5547 0.3 mg/kg (N=54)
Change from baseline in WOMAC pain subscale score									
Baseline	6.43	6.33	6.35	6.10	6.53	5.9	5.7	6.1	6.4
n ¹⁾	71	75	78	77	79	44	47	44	41
Mean ¹⁾ (SD) ¹⁾	-2.43 (2.38)	-3.49 (2.06)	-3.39 (2.44)	-3.07 (2.34)	-3.81 (2.49)	-2.4 (2.18)	-2.7 (1.89)	-3.4 (2.53)	-3.2 (2.24)
LSM ²⁾	-2.25	-3.35	-3.33	-3.03	-3.65	-	-	-	-
Diff. vs. Pbo ³⁾	-	-1.10	-1.08	-0.78	-1.40	-	-0.6	-1.1	-0.8
P value	-	0.0025	0.0029	0.0304	0.0001	-	0.1486	0.0090	0.0488
Change from baseline in WOMAC physical function subscale score									
Baseline	6.15	6.11	6.09	5.94	6.20	5.9	5.9	6.2	6.2

n ¹⁾	70	75	78	76	80	44	47	44	41
Mean ¹⁾ (SD) ¹⁾	-2.12 (2.26)	-3.21 (2.23)	-3.28 (2.29)	-2.97 (2.45)	-3.51 (2.50)	-2.3 (2.30)	-2.9 (1.78)	-3.4 (2.28)	-3.1 (2.18)

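### Does the Week 68 SAP drop the rule that 1 mg q8w is compared only with post-amendment placebo?

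*SAP*

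**What the plan says.** Protocol section 13 (opening text) sets the data rule. The 1 mg q4w arm is evaluated on pooled pre- and post-amendment data, and the 1 mg q8w arm on post-amendment data only. Section 13.3.2(1)(a) builds this into the primary MMRM, and 13.3.2(3) applies the same method to changes from baseline at every assessment time point.

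Week 16 SAP section 8.2.1 (Primary Efficacy Endpoint) has a separate paragraph for each dose between the list of fallback covariance structures and the remark on missing at random. The q8w paragraph begins "Using only the data obtained after the protocol amendment (Ver. 04.00.00000".

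Week 68 SAP section 8.2.1 (Other Efficacy Endpoints) gives almost the same model description, but those two paragraphs are absent: "will be used instead in this order. MMRM that assumes that the missing mechanism is missing at random (MAR) is an analysis method". It continues "This model will be used to estimate the treatment effect in the mFAS when subjects continue receiving treatment through Week 68". Its logistic mixed model (GLMM) for responders refers to "each of the MT-5547 1 mg q4w and MT-5547 1 mg q8w groups compared to the placebo group". Section 3.3 of the same SAP says "For evaluation on 1 mg q8w, analyses will be performed with only the post-amendment data" and gives 142 patients in each of the three arms.

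**The concern.** The Week 68 methods section is where a programmer would look, and the data rule is missing at the point where the Week 16 text has it. Nothing in the section points back to it. The Week 68 SAP cites Week 16 section 8.2.1 only for the testing graph ("Figure 8.2.1-1 in section 8.2.1 of SAP for database at week 16"). The mFAS removes only the 3 mg q4w and 6 mg q8w patients, so pre-amendment placebo patients stay in it. Where this SAP wants a split by amendment period it can say so, as for the baseline table: "summarized by treatment group, and before the protocol amendment and after the protocol amendment on the mFAS population".

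A reader with section 8.2.1 alone might therefore compare q8w with all placebo patients, some of whom could not have been randomised to q8w. Any difference between periods in placebo response, beyond what baseline score, K-L grade and joint explain, would then enter the long-term q8w estimates.

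**Working it through.** **1. The passages side by side**

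| Place | Rule for 1 mg q8w |
|---|---|
| Protocol 13 | post-amendment data only |
| Protocol 13.3.2(1)(a) | post-amendment data only |
| Protocol 13.3.2(3) | same method at each time point |
| Week 16 SAP 8.2.1 | post-amendment data only |
| Week 68 SAP 3.3 | post-amendment data only, 142/142/142 |
| Week 68 SAP 8.2.1 | silent |
| Week 68 SAP 10 | no change from protocol |

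No entry instructs pooling for q8w. The supersession clause in the Week 68 Introduction covers analysis details that the SAP describes. Silence describes nothing, so the protocol rule stands.

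The mFAS and placebo-group wording does not imply pooling either. Week 16 section 8.2.1 refers to the treatment effect in the mFAS directly after imposing the q8w restriction. The Week 16 GLMM text (section 8.2.3) names the placebo group in the same unqualified way, and the Week 16 SAP also has a before/after-amendment baseline table. All three coexist there with the rule.

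The two dose paragraphs could not have been carried over unchanged. They ask for a P value and for the change to Week 16, while Week 68 section 6.2 does no formal tests and the analysis covers all visits.

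**2. The plan's own power figures**

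Inputs from Week 68 SAP 3.3: difference 1.1, SD 2.5, 15% missing at Week 16, 182 per arm (q4w, pooled), 142 per arm (q8w). Two-sided 5% is from Week 16 SAP 8.2.1. Evaluable patients: 0.85 × 182 = 154.7 and 0.85 × 142 = 120.7. SE = 2.5 × √(1/n₁ + 1/n₂); power = Φ(1.1/SE − 1.96).

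| Comparison | SE | Power, single test | Stated |
|---|---|---|---|
| q4w, 182 v 182 | 0.284 | 97.2% | 97% |
| q8w, 142 v 142 | 0.322 | 92.8% | 92% |
| q8w, 142 v 182 (all placebo) | 0.304 | 95.2% | 92% |

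The stated figures are after gatekeeping, and the graph is not shown. Two assumed graphs were simulated with an endpoint correlation of 0.5. A Holm-type graph gives q8w 92.1% (pain) and 86.7% (function) with restricted placebo, and 94.5% and 90.3% with all placebo, against 92% and 87% stated. A fixed sequence taking both q4w hypotheses first gives q8w 91.1% and 88.1% with all placebo, which is also close. The power figures therefore fit the restricted comparator but do not settle the matter; the words and arm sizes in section 3.3 do.

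**3. Size if someone misread section 8.2.1**

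Non-concurrent share of placebo: 40/182 = 22%. Section 3.3 also says "57 patients each were enrolled in the MT-5547 3 mg q4w and 6 mg q8w groups prior to the protocol amendment (Ver. 04.00.00000". If placebo had 57 as well (assuming equal allocation), the share is 57/(142 + 57) = 57/199 = 29%. If 57 is the total for both removed arms, as 506 + 57 = 563 implies, it is 28.5 per arm: 28.5/170.5 = 17%.

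Shift in the q8w estimate = share × d, where d is the period difference in placebo change left after adjustment. The documents give no d, so the range is assumed:

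| d | share 17% | share 22% | share 29% |
|---|---|---|---|
| 0.25 | 0.04 | 0.05 | 0.07 |
| 0.5 | 0.08 | 0.11 | 0.14 |
| 1.0 | 0.17 | 0.22 | 0.29 |

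The largest entry needs a drift close to the whole planned effect of 1.1. It is still below the minimum important difference of 0.67 to 0.75 cited in section 3.3. The restricted comparison has an SE about 6% larger: 0.322/0.304 = 1.06.

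**The case for a change.** The strongest argument for a change concerns timing and placement. The Week 68 SAP reports the Week 24 analysis as already done, and the sponsor's key was to be opened once Week 24 data were fixed. A plan finalised then should leave no choice of comparator open, and a sentence in a sample-size section is a weak place for an analysis rule. Drift is also conceivable. A safety recommendation fell between the periods, and the chance of active treatment went from 3 in 4 (if allocation was equal) to 2 in 3. The planned checks of homogeneity cover baseline and Week 16 outcomes, nothing later.

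The wording point stands: section 8.2.1 would be easier to use if it repeated the rule, and for the GLMM the rule rests only on the general statements in protocol section 13 and SAP section 3.3. But the choice was not open. Version 4.0 of the protocol, dated 31 July 2018, fixed it well before any unblinded Week 24 result, and nothing in the Week 68 SAP withdraws it. Section 3.3 states it as a rule for the analyses as well as an input to power. The SAS code is not visible, so the documents cannot show that anyone pooled.

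**Conclusion.** The concern does not call for a change. Week 68 SAP section 8.2.1 omits a rule that the same SAP states in section 3.3 and that the protocol imposes at every time point. Read together, the documents give one comparator for 1 mg q8w: post-amendment placebo, 142 planned. Restoring the text would only repeat this, and copying the Week 16 paragraphs word for word would bring back P values that section 6.2 excludes.

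If the section were misread, the long-term q8w estimates would move by about 0.22d, or 0.05 to 0.22 points for an assumed d of 0.25 to 1.0 (0.04 to 0.29 over the possible shares). These are descriptive estimates with confidence intervals, and between Weeks 16 and 48 the placebo arm also receives naproxen. The confirmatory Week 16 tests have their own explicit rule. The conclusion assumes that the unseen code follows section 3.3; nothing in the documents suggests otherwise.
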